Protocol Number: 20240175

Date: 27 March 2025 **Page 1 of 47**

Summary Table of Study Protocol

Title	Real World Evaluation of Sotorasib among Chinese Non-Small Cell Lung Cancer Patients	
Protocol version identifier	20240175, Original Protocol, Version 1.0	
Date of last version of the protocol	27 March 2025	
EU Post Authorization Study Register No	Not Applicable (NA)	
Active Substance	Sotorasib	
Medicinal Product	LUMAKRAS® (sotorasib)	
Device	Not Applicable (NA)	
Product Reference	AMG 510	
Procedure Number	Not Applicable (NA)	
Joint PASS	No	
Research Question and Objectives	Among Chinese patients with KRAS p.G12C-mutated locally advanced or metastatic NSCLC, who have received at least 1 prior systemic therapy: • Primary Objective: • Characterize the safety profile of sotorasib. • Secondary Objective: • Describe real-world overall survival (OS) of sotorasib. • Exploratory Objective: • CCI	
Country of Study	China	
Authors	PPD	

Protocol Number: 20240175

Date: 27 March 2025 Page 2 of 47

Marketing Authorization Holder

Marketing Authorization Holder(s)	Amgen Inc
Marketing Authorization Holder Contact	[name]
	[name]
	[name]

This protocol was developed, reviewed, and approved in accordance with Amgen's standard operating procedures.

Confidentiality Notice

This document contains confidential information of Amgen Inc.

This document must not be disclosed to anyone other than the site study staff and members of the Institutional Review Board/Independent Ethics Committee/Institutional Scientific Review Board or equivalent, as applicable.

The information in this document cannot be used for any purpose other than the evaluation or conduct of the research without the prior written consent of Amgen Inc.

If you have questions regarding how this document may be used or shared, call the Amgen Medical Information number: United States, [name]. Amgen's general number in the United States ([name]).

Protocol Number: 20240175

Date: 27 March 2025 **Page 3 of 47**

Investigator's Agreement

I have read the attached protocol entitled Real World Evaluation of Sotorasib among Chinese Non-Small Cell Lung Cancer Patients, dated 27 March 2025, and agree to abide by all provisions set forth therein.

Study feasibility within each available data source in China was evaluated in terms of available infrastructure to support execution of a real-world study, accessible data, ethical and security requirements, coverage and accuracy of critical covariates, completeness of follow-up for outcomes, and sample size of the target patient population. Based upon this evaluation, data sources in BOAO Pilot Zone and Hong Kong SAR were selected to be the most relevant to address the study objectives.

Protocol Number: 20240175

Date: 27 March 2025 **Page 11 of 47**

Objectives

Objectives	Endpoints		
Primary			
Characterize the safety profile of sotorasib.	The patient incidence of adverse events (AE) after sotorasib initiation, including:		
	 Treatment-emergent adverse events (TEAE) 		
	 Adverse event of interest, inclusive of hepatotoxicity, interstitial lung disease/pneumonitis, and renal toxicity 		
	o Treatment-related AEs		
	 Treatment-related AEs of grade 3 or worse 		
	o Serious treatment-related AEs		
	 Treatment-related AEs leading to treatment discontinuation 		
	 Treatment-related AEs leading to dose reduction 		
	 Treatment-related AEs leading to death 		
Secondary			
Describe real-world OS of sotorasib	OS from initial date of sotorasib use to date of death		
Exploratory			
CCI			

Hypothesis

Study objectives are descriptive in nature; no hypothesis will be tested.

Study Design

The study design is a retrospective cohort followed longitudinally for safety and effectiveness endpoints, based upon review of medical charts.

Protocol Number: 20240175

Date: 27 March 2025 Page 12 of 47

Study Population or Data Source

The target population is adult patients with *KRAS p.G12C*-mutated locally advanced or metastatic NSCLC and previously treated with at least 1 prior systemic therapy that have received sotorasib treatment in either location of BOAO Pilot Zone and Hong Kong SAR.

In BOAO Pilot Zone, patients, often residing from across mainland China, need to be physically admitted to one of the several hospitals in BOAO Pilot Zone to receive sotorasib. The first hospitalization includes a complete medical history, radiology scans, tumor biomarker assessment, and liver and renal function tests to inform clinicians' decision to treat. As sotorasib is in the pre-registration program, the government requires close monitoring and reporting of safety events, which are well documented in the established hospital system. Hence, expectation that safety endpoints will be measured adequately in this study. As sotorasib is an oral medication taken daily until disease progression or unacceptable toxicity, patients need to physically return to the BOAO Pilot Zone hospital at least once per month initially, and every 3 months thereafter, to continue therapy. A case report form created for this study will be used to extract the relevant structured and unstructured data from the electronic heath record.

In Hong Kong SAR, the Clinical Data Analysis and Reporting System (CDARS) database will be used to identify patients treated with sotorasib at any public hospital. CDARS is a population-based database covering residents in Hong Kong SAR and can be linked to mortality records. Hence, the expectation that OS will be measured with complete follow-up. While the structure data within CDARS will provide most of the relevant data for study, the unstructured clinical notes within the electronic health record (Electronic Patient Record/Clinical Management System [EPR/CMS]) will also be used to augment information on key covariates.

Summary of Patient Eligibility Criteria

Inclusion Criteria:

- Adult (≥ 18 years) as of the index date.
- KRAS p.G12C-mutated locally advanced or metastatic NSCLC
- Received at least 1 dose of sotorasib.
- Receipt of at least 1 prior systemic therapy before use of sotorasib
- Obtained informed consent form (ICF), if required.

Exclusion Criteria:

Documentation of being a non-Chinese ethnicity.

Protocol Number: 20240175

Date: 27 March 2025 **Page 13 of 47**

Follow-up

Index date: sotorasib initiation date.

For objective of safety, CC

follow-up per patient

will continue through earliest date of:

- Last clinical activity in the data source
- Data cut-off in the data source:
 - BOAO Pilot Zone: Ethics Committee (EC) submission date
 (~ Q2 2025)
 - Hong Kong SAR: Data extraction cut-off date (~ Q3 2025)
- Death
- Last treatment with sotorasib + 30 days

As the Hong Kong SAR CDARS database is a closed-loop database with linkage to the regional deaths registry, patients without evidence of death in the CDARS database by the data cut-off date were considered alive, and their last activity date will be the same as the cut-off date.

For objective of OS, follow-up per patient will continue through earliest date of last clinical activity in the data source, data cut-off in the data source, or death.

Variables

Outcomes:

- Primary: The patient incidence of AEs after sotorasib initiation.
- Secondary: OS from clinician notes in electronic health record and linkage to mortality records (where available).
- Exploratory: CCI

 CCI

Exposure:

o Use of sotorasib

Protocol Number: 20240175

Date: 27 March 2025 **Page 14 of 47**

Covariates

Key demographic, clinical characteristics, and pathology covariates including and not limited to age, sex, smoking status, body mass index (BMI), Eastern Cooperative Oncology Group (ECOG) performance status, histology, tumor stage, programmed death-ligand 1 (PD-L1) protein expression, presence of tumor mutations or rearrangements, laboratory test, electrocardiogram (ECG) and radiology, prior systemic treatments, brain metastases (if information available), prior lines of systemic therapy, and concomitant medications.

Study Sample Size

By the time of data cut-off, an estimated about 100 and 15 patients will have been treated with sotorasib and eligible for study inclusion from BOAO Pilot Zone and Hong Kong SAR, respectively. For a sample size of 115 patients and the observation of a proportion of 50% patients with an endpoint the largest level of margin of error (indicating the lowest level of precision) is \pm 9.14%.

Data Analysis

Frequencies will be presented for categorical demographic, clinical, and pathological variables. Descriptive statistics (mean, median, standard deviation, and range) will be presented for continuous variables.

The patient incidence of AEs will be summarized by count and proportions, specifically the proportion of patients experiencing AEs relative to the total number of patients. Median OS and PFS, along with the corresponding 95% confidence intervals (CIs) will be calculated using Kaplan-Meier estimates. The estimated survival probabilities, along with the corresponding 95% CIs will be presented for patients at 6 and 12 months.

CC

5. Amendments and Updates

None

6. Rationale and Background

6.1 Diseases and Therapeutic Area

Lung cancer is the leading cause of cancer death worldwide (Sung et al, 2021). In 2022, an estimated 1 060 600 new cases of lung cancer and 733 300 people died in China (Han et al, 2024). The 5-year relative survival rate for lung cancer is approximately 19.7% (Zeng et al, 2018).

Protocol Number: 20240175

Date: 27 March 2025 **Page 15 of 47**

The RAS proto-oncogene has been identified as an oncogenic driver of tumorigenesis in several cancers, including NSCLC. Different tumor types are associated with mutations in certain isoforms of *RAS*, with KRAS being the most frequently mutated isoform in most cancers (Prior et al, 2012). The *KRAS p.G12C*-mutation is estimated to occur in approximately 13% of lung adenocarcinoma (including NSCLC), 3% of colorectal cancer , and 1% to 2% of numerous other solid tumors (including pancreatic, endometrial, bladder, ovarian, and small cell lung tumors) in the western population (The AACR Project GENIE Consortium, 2017; Biernacka et al, 2016; Neumann et al, 2009). *KRAS p.G12C*-mutation is less prevalent in the Asian population compared to the Western population. It was estimated that the prevalence of *KRAS p.G12C*-mutation ranges from 3% to 4.6% in Chinese NSLSC (Liu SY et al, 2020; Liu Y et al, 2021; Loong et al, 2020; Chen et al, 2022).

Patients with stage VI or advanced stage IIIB/C NSCLC are usually treated in the first line setting with platinum-based doublet therapy and/or checkpoint inhibitors either alone or in combination. Patients whose tumors have actionable mutations or alterations (eg, epithelial growth factor receptor [EGFR], anaplastic lymphoma kinase [ALK], ROS, and BRAF) will receive targeted therapies directed at these specific molecular targets (Ettinger et al, 2022).

In the 2L+ setting for advanced NSCLC in China, patients are typically treated with docetaxel, pemetrexed, or erlotinib (Oncology Society of Chinese Medical Association, 2023). Only 1 *KRAS p.G12C* inhibitor, fulzerasib, received conditional approval by National Medical Products Administration (NMPA) for the treatment of *KRAS p.G12C*-mutated NSCLC in August 2024 in China, although it has not been made commercially available as of September 2024 (NMPA 2024).

6.2 Rationale

In the single-arm phase II trial CodeBreaK 100 for patients with *KRAS p.G12C*—mutated advanced NSCLC previously treated with standard therapies, the median OS was 12.5 months (95% CI, 10.0 to not evaluable), with treatment-related AEs occurring in 69.8% of patients, including grade 3 events in 19.8% of patients (Skoulidis et al, 2021). In the phase III trial CodeBreak 200 comparing sotorasib with docetaxel (first randomized Phase 3 clinical trial of a *KRAS p.G12C* inhibitor) in patients with advanced NSCLC who had progressed after prior platinum-based chemotherapy and a programmed cell death 1 (PD-1) or programmed death-ligand 1(PD-L1) inhibitor,

Protocol Number: 20240175

Date: 27 March 2025 Page 16 of 47

sotorasib demonstrated good tolerability, with fewer grade 3 or worse events (33% vs. 40%) and fewer serious treatment-related AEs compared to docetaxel (11% vs. 23%), along with better PFS (5.6 months [95% CI 4.3–7.8] vs 4.5 months [3.0-5.7]) and similar OS compared to the docetaxel group (10.6 months [95% CI 8.9-14.0] vs 11.3 months [95% CI 9.0–14.9]). Consistent findings were demonstrated in RWE studies (Thummalapalli R et al, 2023; de Langen AJ et al, 2023), providing valuable context for the results of the current study.

On May 28, 2021, sotorasib was granted accelerated approval in the US by the FDA for adult patients with *KRAS p.G12C*-mutated locally advanced or metastatic NSCLC who have received at least 1 prior systemic therapy (de Langen AJ et al, 2023).

Within the Greater China region, of Chinese population, sotorasib was approved in Hong Kong on April 29, 2022, with indication as monotherapy for the treatment of adult patients with *KRAS p.G12C*-mutated locally advanced or metastatic NSCLC, who have progressed on, or are intolerant to, platinum-based chemotherapy and/or anti-PD-1/LD-L1 immunotherapy. Subsequently, it was approved in Taiwan on June 14, 2022, with indication for the treatment of adult patients with *KRAS p.G12C*-mutated locally advanced or metastatic NSCLC who have received at least 1 prior systemic therapy. Sotorasib has not been approved in mainland China but has been used in BOAO Pilot Zone (Hainan Province, China) since August 2021 through pre-registration program in BOAO Pilot Zone, strictly following FDA approved label. There are no published data on the safety and effectiveness of sotorasib among Chinese patients in real-world and clinical settings. We aim to characterize the safety profile, real-world OS (Lasiter et al, 2022) CCL (Khozin et al, 2019) of sotorasib.

6.3 Feasibility (fit-for-purpose evaluation)

Active and accessible data:

As introduced in Section 6.2, sotorasib became available in BOAO Pilot Zone in August 2021 through a pre-registration program. Sotorasib will be continuously available at BOAO Pilot Zone before data cut-off (~Q2 2025). BOAO Pilot Zone is the only place in mainland China with sotorasib access and thus enable a complete capture of all mainland Chinese patients treated with sotorasib in real-world and clinical settings.

Protocol Number: 20240175

Date: 27 March 2025 Page 17 of 47

Patient-level data in BOAO Pilot Zone will be available and submitted to enable a regulatory authority to reproduce the results.

The Hong Kong SAR Clinical Data Analysis and Reporting System (CDARS) database will be used to extract patients treated with sotorasib in Hong Kong SAR. Clinical Data Analysis and Reporting System is a population-based database with medical records covering residents in Hong Kong SAR who received care from any public hospital. It also contains data on causes of death through its internal linkage to regional deaths registry and have been used in various disease area including lung cancer (Philip et al, 2024). Academic researchers in Hong Kong SAR will be able to apply and access the database. The database is used for efficiency; however, the information is drawn from detailed patient records, ensuring that the analysis is based on comprehensive and accurate medical chart data. Details of data sources are provided in Section 8.4.

Ethical and security requirements

The study will follow requirements of the governance and sites. All data extracted will be anonymized. The study protocol will be reviewed by the IRB of each site in BOAO Pilot Zone and Hong Kong University in Hong Kong SAR. In addition to governance and the IRB, the study will comply with Amgen's global standard operation procedures and technical governance for observational research. The International collaboration Human Genetics Resources Administration of China application will be submitted for BOAO Pilot Zone. Details are provided in Section 9.

Coverage of critical variables

The electronic health record database in BOAO Pilot Zone participating hospitals contain critical data relevant to the research question, for example the exposure of sotorasib, AEs, effectiveness outcomes, and key covariates. The electronic medical record (EMR) system in Hong Kong SAR contains both structured data, including demographic information, diagnosis, prescription records, procedure, hospital stay, discharge information, and unstructured data, including genetic testing results, radiographical and imaging exam results and additional patient information. Critical variables are covered and will be extracted to the extent possible.

Accuracy of the definition of exposure, outcomes, and covariates

Eligible patients need to be physically at BOAO Pilot Zone hospitals to receive treatments, enabling complete sotorasib exposure assessment in electronic health record databases. In addition, as advanced NSCLC is a life-threating disease which

Protocol Number: 20240175

Date: 27 March 2025 **Page 18 of 47**

needs close support from physicians specialized in treating NSCLC, it is expected that patients remain at same site in BOAO Pilot Zone for treatment. As sotorasib is used through the pre-registration program, local government authorities require close monitoring and reporting of safety events which were well documented in hospitals by physicians. Besides, physicians were reported to proactively follow-up with patients and document patients' treatment information, follow-up evaluations (both within and outside BOAO Pilot Zone), safety events, treatment outcome and discontinuation in hospital electronic health record database. These real-time data sources will be used to extract comprehensive and accurate outcome and key covariates.

Data will be verified using the data source by the study monitor and reviewed for consistency. All data extracted will be approved by the investigator at the investigational center. Adverse event grades and relationship to sotorasib may be unavailable or unconfirmable for some patients due to limitations in the available information. The level of missingness will be described and results related with grade will be interpreted with caution.

Sample size

The feasibility check indicates that at the data cut-off, approximately 100 sotorasib treated patients in BOAO Pilot Zone, and about 15 patients in Hong Kong SAR, will be eligible for inclusion. Details of sample size calculation are provided in Section 8.5.

Representativeness of the target population

All patients meeting the eligible criteria in BOAO Pilot Zone and in public hospitals in Hong Kong SAR will be included, unless demonstrated operationally unfeasible. This approach will enhance the representativeness of the study's target population across China.

Taiwan was not selected because sotorasib is not reimbursed in Taiwan and individual site chart review of a marketed medication won't capture information outside of that individual site (ie, concern of lost follow up and missing death information).

6.4 Statistical Inference (Estimation)

The objectives of this study are descriptive in nature and will only include estimations, no hypotheses will be tested.

Protocol Number: 20240175

Date: 27 March 2025 Page 19 of 47

7. Research Question and Objectives

7.1 Primary

To characterize the safety profile of sotorasib in Chinese patients with *KRAS p.G12C*-mutated locally advanced or metastatic NSCLC, who have received at least 1 prior systemic therapy.

7.2 Secondary

To describe real-world OS of sotorasib in Chinese patients with *KRAS p.G12C*-mutated locally advanced or metastatic NSCLC, who have received at least 1 prior systemic therapy.

7.3 Exploratory

8. Research Methods

8.1 Study Design

This is a retrospective medical chart review study of Chinese patients treated with sotorasib in real-world and clinical settings in BOAO Pilot Zone and Hong Kong SAR.

8.2 Setting and Study Population

Two regions will be included in the study, ie, BOAO Pilot Zone and Hong Kong SAR.

Until data cut-off date, approximately 100 sotorasib treated patients in Hainan BOAO Pilot Zone, and about 15 patients in Hong Kong SAR, will be eligible for medical chart review. Details of data sources are provided in Section 8.4.

8.2.1 Study Period

The study eligibility period extends from the patients' index date (ie, the initiation of sotorasib) to the end of study period, defined as the earliest occurrence of patient's last activity date in the data source, data cut-off date or death.

The first available sotorasib use in BOAO Pilot Zone is around August 2021 through a pre-registration program. Specifically, sotorasib was included in the following hospitals'

Protocol Number: 20240175

Date: 27 March 2025 **Page 20 of 47**

drug lists and available for prescription: Ruijin Hainan Hospital in July 2022; BOAO Super Hospital in August 2021; BOAO Hengda Hospital in November 2021; and BOAO future Hospital in January 2022. The data cut-off will be the EC submission date (~ Q2 2025).

Sotorasib was approved in Hong Kong on April 29, 2022. The eligible treatment should occur after April 29, 2022. The data cut-off will be the date of data extraction (~ Q3 2025).

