8.2.6 Study Follow-up

As the Hong Kong SAR CDARS database is a closed-loop database with linkage to the regional deaths registry, patients without evidence of death in the CDARS database by the data cut-off date were considered alive, and their last activity date will be the same as the cut-off date.

For the objective of OS, follow-up per patient will continue through earliest date of last clinical activity in the data source, data cut-off in the data source, or death.

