8.3.2 Outcome Assessment

Safety Outcomes

In BOAO Pilot Zone, the AEs recorded in the electronic health record database throughout the study period will be documented and analyzed. Detailed information in medical records including vital signs, concomitant treatments, results of routine laboratory testing, ECG, and radiology will be reviewed to verify these AEs. Severity grade of AEs will be further verified by investigators according to the Common Terminology Criteria for Adverse Events (CTCAE), version 5.0 (CTCAE v5.0).

The patient incidence of AE after sotorasib initiation, including:

- TEAE
- Adverse event of interest, inclusive of hepatotoxicity, interstitial lung disease/pneumonitis, and renal toxicity
- Treatment-related AEs
- Treatment-related AEs of grade 3 or worse
- Serious treatment-related AEs
- Treatment-related AEs leading to treatment discontinuation
- Treatment-related AEs leading to dose reduction
- Treatment-related AEs leading to death

[figure not shown]
In Hong Kong SAR CDARS database, only adverse event of interest, inclusive of hepatotoxicity, interstitial lung disease/pneumonitis, and renal toxicity will be documented and analyzed. Each event of interest is a grouping of individual preferred terms determined using the following standardized MedDRA queries (SMQs): drug-related hepatic disorders – comprehensive search (SMQ narrow) for hepatotoxicity; interstitial lung disease (SMQ narrow) for ILD/pneumonitis; and acute renal failure (SMQ narrow) for renal toxicity. Medical records including diagnosis, vital signs, concomitant treatments, results of routine laboratory testing, ECG, and radiology will be reviewed to identify and verify AE. Detailed testing and exams to review will be further clarified in the statistical analysis plan and eCRF.

Protocol Number: 20240175

Date: 27 March 2025 Page 23 of 47

OS

• OS: The time from the index date to death from any cause. Patients without evidence of death at data cutoff will be right-censored at their last activity date.

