8.4 Data Sources

In BOAO Pilot Zone, patients, often residing from across mainland China, need to be physically admitted to one of the several hospitals in BOAO Pilot Zone to receive sotorasib. The first hospitalization includes a complete medical history, radiology scans, tumor biomarker assessment, and liver and renal function tests to inform clinicians' decision to treat. As sotorasib is in the pre-registration program, the government requires close monitoring and reporting of safety events, which are well documented in the established hospital system. Hence, expectation that safety endpoints will be measured adequately in this study. As sotorasib is an oral medication taken daily until disease progression or unacceptable toxicity, patients need to physically return to the BOAO Pilot Zone hospital at least once per month initially, and every 3 months thereafter based on physician's assessment and justification, to continue therapy. Patients seeking refills require recent radiology results, organ function evaluation etc. reassessment. Refills can be initiated with online evaluations and subsequently processed through outpatient clinics at hospitals in Hainan. Reports from Tier A hospitals across China are accepted. A case report form created for this study will be used to extract the relevant structured and unstructured data from the electronic heath record.

In Hong Kong SAR, this study will be using the electronic health records of the CDARS database managed by the Hong Kong Hospital Authority, a statutory body in charge of all public hospitals and their ambulatory clinics in Hong Kong SAR. Anonymized patient data are transferred daily to CDARS for audit purposes from the clinical management system (CMS) of the Hospital Authority, which contains medical records including: demographic information, diagnoses, prescription records, laboratory tests, accident and emergency attendance, outpatient clinics, hospital stay, and discharge information of patients since 1993. It also contains data on causes of death through its internal linkage

Protocol Number: 20240175

Date: 27 March 2025 Page 26 of 47

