to regional deaths registry from the Immigration Department. Hence, expectation that OS will be measured with complete follow-up. A unique reference number is assigned to each patient for identification and data retrieval purposes. The structure data within CDARS will provide most of the relevant data for study, the unstructured clinical notes within the electronic health record (Electronic Patient Record/Clinical Management System [EPR/CMS]) will also be used to augment information on key covariates. Electronic patient record (EPR) consolidates individual patient health records from various sources, including hospitals, clinics, and primary care providers, into a single electronic record, providing a comprehensive view of a patient's medical history.

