8.5 Study Sample Size

This is a descriptive study in which patient-level data on safety, OS, CCI

By the time of data cut-off, there will be approximately 100 sotorasib treated patients in BOAO Pilot Zone assuming all sites are eligible, and about 15 patients in Hong Kong SAR, will be eligible for enrollment.

The estimation precision of parameters is provided based on the preliminary sample count of all patients treated with sotorasib in BOAO Pilot Zone and Hong Kong SAR. The formular, based on the normal approximation to the binomial distribution, for calculating the precision (ie, margin of error, which is represented by one half the desired width of the confidence interval) given a proportion and sample size is as the following:

$$e = \sqrt{\frac{px (1-p)x (Z_{1-\frac{\alpha}{2}})^{2}}{n}}$$

Where P is the expected proportion of interest, n is the sample size, and $Z_{1-\frac{\alpha}{2}}$ is the standard normal Z value corresponding to a cumulative probability of $(1-\frac{\alpha}{2})$ (eg, if α = 0.05 then Z=1.96). The following table (Table 1) provides the estimated precision based on the sample size of patients who received sotorasib (N = 115, tentatively) and various proportions of interest.

Protocol Number: 20240175

Date: 27 March 2025 Page 27 of 47

Table 1. Precision based on the sample size by various proportions

Proportion (1- proportion)	Sample size of patients	The margin of error (absolute precision)
50% (50%)	115	9.14%
40% (60%)	115	8.95%
30% (70%)	115	8.38%
20% (80%)	115	7.31%
10% (90%)	115	5.48%

As the proportion of interest (p) (eg, proportion of treatment-related AEs of grade 3 or worse) in this study is not known in advance, we consider the proportion to be 50% (maximum uncertainty). Such an assumption yields the most conservative, ie, the largest level of margin of error (indicating the lowest level of precision), with is $\pm 9.14\%$.

The sample size of patients treated with sotorasib will be confirmed during data cleaning and data analysis phase.

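### Hong Kong overall survival is censored on the extraction day itself, so a death not yet visible in CDARS that day is counted as survival time

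*Protocol*

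**What the plan says.** Three statements together fix the rule for Hong Kong.

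- **Cut-off (Protocol 8.2.1).** "The data cut-off will be the date of data extraction (~ Q3 2025".
- **Vital status (8.2.6, repeated in the Abstract and under the Study Design Schema).** "patients without evidence of death in the CDARS database by the data cut-off date were considered alive". Such a patient is then given the cut-off as the day of last activity.
- **Censoring (8.3.2).** "Patients without evidence of death at data cutoff will be right-censored at their last activity date".

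The justification is in 8.4, where CDARS is described as internally linked "to regional deaths registry from the Immigration Department. Hence, expectation that OS will be measured with complete follow-up". The same section says "Anonymized patient data are transferred daily to CDARS for audit purposes", and the source it names for that transfer is the Hospital Authority's clinical management system. The protocol gives no refresh interval, registration delay or date of completeness for the death-registry link. Section 8.5 expects "about 15 patients in Hong Kong SAR, will be eligible for enrollment", and 8.7.2.1 has the two regions analysed separately.

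**The concern.** Treating the absence of a death record as proof of life is sound up to the date through which death data are complete. The protocol applies it up to the day of extraction without showing that the two dates coincide. Daily transfer is described for hospital records. A death outside the public hospitals depends on registration and then on the registry link, and nothing is said about how fast that link is.

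Ordinary censoring at last contact would stop such a patient's clock early. This rule runs it on to extraction day. Each missed death removes an event and adds false survival time, so the error goes one way only.

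The planned sensitivity analyses cannot reveal it. The one in 8.7.2.5.3 excludes patients whose last activity precedes the cut-off, and no Hong Kong survivor can meet that condition because last activity is set to the cut-off. The one in 8.9.3 follows patients without a death to the end of the study, which the Hong Kong main analysis already does.

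At stake is the Hong Kong OS estimate, in the region on which the protocol relies for complete mortality follow-up.

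**Working it through.** **The plan's own figure.** The only precision figure is Table 1: 1.96 × √(0.5 × 0.5 / 115) = 0.0914, or 9.14%, as printed. It concerns proportions in 115 pooled patients and does not bear on Hong Kong OS. The protocol gives no figure for the Hong Kong OS estimate or for the linkage delay.

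**Inputs from the protocol**
- n = 15 Hong Kong patients (8.5).
- Eligible treatment after 29 April 2022, extraction about Q3 2025 (8.2.1). T = 41 months if extraction falls at the end of that quarter.
- Median OS of 10.6 months (95% CI 8.9 to 14.0) in the cited phase III trial (Abstract), used only as a planning value.

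**Assumptions**
- Exponential survival and even entry over T.
- A delay L of 0, 1, 2 or 3 months, because the documents give none.
- Every death in the last L months unseen in CDARS. This makes the results a ceiling for each L.

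**Expected deaths**
- λ = ln 2 / 10.6 = 0.0654 per month, so λT = 2.68.
- Expected alive at extraction = 15 × (1 − e^(−λT)) / (λT) = 15 × (1 − 0.0685) / 2.68 = 5.2.
- Expected dead = 15 − 5.2 = 9.8.

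**Expected deaths inside the delay**
- Formula: (15 / T) × [L − (e^(−λ(T−L)) − e^(−λT)) / λ].
- L = 1: (15 / 41) × (1 − 0.071) = 0.34.
- L = 2: (15 / 41) × (2 − 0.146) = 0.68.
- L = 3: (15 / 41) × (3 − 0.227) = 1.01.
- As shares of 9.8 deaths: about 3%, 7% and 10%.

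**Effect on the Kaplan-Meier summaries.** The protocol's rule was applied to 500,000 simulated patients per scenario, with T = 41 and a true median of 10.6 months.

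| Delay (months) | Missed deaths per 15 | Chance of at least one | Median read (months) | 12-month OS read |
|---|---|---|---|---|
| 0 | 0 | 0% | 10.6 | 45.6% |
| 1 | 0.34 | 29% | 10.9 | 46.7% |
| 2 | 0.68 | 50% | 11.3 | 47.8% |
| 3 | 1.01 | 65% | 11.7 | 49.1% |

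Each missed death adds on average L/2 months of false survival time.

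**Sensitivity, all at a 3-month delay**
- With T = 40, a true median of 8.9 reads 9.8 and a true median of 14.0 reads 15.6.
- If half the patients start in the last 12 of 40 months and the true median is 10.6, then 1.26 deaths are missed and the median reads 12.7.

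**Sampling error for comparison.** With 15 patients, T = 40 and no delay, the simulated 95% range of the Kaplan-Meier median is about 4.5 to 25 months.

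**After the change.** With censoring moved back by L, the median reads about 10.6 months and 12-month OS about 45.6% at every delay above.

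**The case against.** The best reply is that CDARS holds more than the registry link. The rule in 8.2.6 turns on any evidence of death in CDARS. Section 8.4 has hospital-stay, discharge and emergency-attendance records arriving daily, and the Abstract draws OS from clinician notes as well as linked mortality records. A death in a public hospital may therefore show without the registry. This stands. A reader might infer that everyone without a linked death is counted alive, but the text does not say so. The exposed group is deaths that are both outside hospital records and not yet linked, and its size is not documented. That is why the counts above are ceilings.

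Second, no delay is documented, and with none there is no bias. This also stands. The 1 to 3 months are assumptions.

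Third, 8.9.4 concedes that death information may be incomplete because only reported deaths are used, in a paragraph that mentions both regions. That is a general caveat. It does not name the delay or change the censoring rule, and 8.4 still says of Hong Kong "Hence, expectation that OS will be measured with complete follow-up".

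Fourth, the Abstract words the Hong Kong cut-off more loosely, which might allow a date before extraction. Section 8.2.1 is explicit, and because the protocol itself fixes the rule, this is not a detail left open for the analysis plan.

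A reader might also extend the point to adverse events of interest during a hospital stay still open at extraction. The documents do not support that. Section 8.3.2 identifies these events from diagnoses, vital signs, concomitant treatments, laboratory results, ECG and radiology, so it does not depend on discharge information.

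**Conclusion.** The point holds as a minor one. As written, the rule converts any death not yet visible in CDARS on extraction day into survival time, always in the favourable direction, and no planned analysis would show it. Its size depends on a delay that the documents do not state. It ranges from no bias at zero delay to a ceiling of about one missed death in 9.8, and a median of 11.7 instead of 10.6 months, at 3 months. These figures assume even entry over 41 months and exponential survival. Later entry raises the ceiling.

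The effect is confined to a descriptive secondary endpoint in about 15 patients and is small beside their sampling error. The BOAO estimate, the primary safety endpoint and Table 1 are untouched. A reader might conclude that Hong Kong OS is materially inflated, but the documents do not support that, because they show neither a delay above zero nor how many deaths fall outside hospital records. The case for acting is that the error is systematic and cheap to remove.

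**What to change.** Change 8.2.1 and 8.2.6 for Hong Kong OS only. Suggested wording:

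> For Hong Kong SAR, overall survival is censored administratively at a fixed calendar date that precedes data extraction by at least the death registration and linkage delay confirmed with the data holder. The delay and the date are stated. Deaths are counted only up to that date, and patients with no evidence of death up to that date are considered alive on it. The cut-off for safety remains the extraction date.

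The delay has to come from the data holder. Three months is used here only to illustrate.

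**Cost.** A sentence or two and one enquiry. OS follow-up shortens by the chosen delay for patients still alive, about 5 of 15 on the assumptions above. Patients who start inside the window add nothing to OS: 15 × 3 / 41 = 1.1 patients at 3 months, or 15 × 1 / 41 = 0.4 at 1 month. Moving the whole Hong Kong cut-off back would also drop those patients from the primary safety analysis, which is why the change should be limited to OS.
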